7. BMI
8. Underweight
9. Anemia
10. Abnormal score on MoCA
11. Frailty Index, based on accumulation of deficits model

2.1 Univariate analysis:

Comparison of groups at baseline

1. Patients with sinus rhythm at baseline
2. Patients with known AF at baseline

2.2 Univariate analysis:

Comparison of sensitivity and specificity of the bleeding risk assessment scores

1. Comparing Area Under the ROC curve
2. Comparing sensitivity, specificity and predictive values at the per score predefined cut-off values

3.1 Univariate analysis

Comparison of groups including follow up data

1. Patients with sinus rhythm during entire study
2. Patients with newly detected AF

Correction for age if necessary

3.2 Multivariate analysis

Correction/multivariate analysis of significant differences found in the univariate analysis 3.1

4. Multivariate analysis / Regression analysis

1. Factors predicting newly detected AF
2. NT-proBNP and/or GDF-15 predicting newly detected AF
3. Factors predicting death, or major bleeding, or composite outcome (death + major bleeding)

References

3. Zwart LAR, Jansen RWMM, Germans T, Simsek S, Ruiter JH, Hemels MEW. Opportunistic screening for atrial fibrillation with a single lead device in geriatric patients. Journal of Geriatric Cardiology (2020) 17: 149-154.
5. Rockwood K and Mitnitski A. Frailty in relation to the accumulation of deficits. Journal of Gerontology 2007, Vol. 62A, No. 7, 722-727.
7. Riezebos K et al. Article in press in HRS Cardiovascular Digital Health Journal.

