Photo-plethysmography (PPG) is a promising technology used in smartphones and smartwatches for heartrate and rhythm assessment. (6) To retrieve PPG measurements a photo-emitter of infrared light is coupled to a photo-receiver. The amount of infrared light absorbed or reflected by blood represents the systolic and diastolic phase. This technology has low costs and does not require additional hardware. Although easy to use and widely available, PPG measurements require good signal quality which may be affected by poorly perfused tissue or tremors. Especially in AF detection proper signal-noise assessment is important because of the irregular depolarization of the ventricles. To overcome these previous issues, we developed an automated PPG based diagnostic algorithm for the smartphone to detect AF. The test characteristics of this technique are robust and described elsewhere. (7)

Principal investigators and steering committee:

Dr. [name], cardiologist, Rijnstate hospital Arnhem

Dr. [name], geriatrician, North West Clinics, Alkmaar

Dr. [name], cardiologist Rijnstate hospital, Arnhem

Dr. [name], cardiologist, OLVG, Amsterdam

Dr [name], cardiologist, North West Clinics, Alkmaar

Participating centers:

Dijklander Hospital, Hoorn. Drs. [name], geriatrician.

Meander Medical Centre, Amersfoort. Drs. [name], geriatrician.

North West Clinics, Alkmaar. [name][name], geriatrician.

Rijnstate Hospital, Arnhem. [name], geriatrician.

Onze Lieve Vrouwe Gasthuis, Amsterdam. [name], cardiologist.

Aims of the project:

- a. To determine the rate of newly detected AF with repeated screening using a PPG based smartphone AF detection algorithm during follow-up visits at a geriatric outpatient center.
- b. To determine the rate of (paroxysmal) AF during follow-up visits.
- c. To evaluate the predictive value of a single measurement of NTproBNP at the baseline evaluation for the development of new AF.
- d. To evaluate the predictive value of the ABC Bleeding Risk Score, compared to the ATRIA Bleeding Risk Score, ORBIT Bleeding Risk Score, and HASBLED score.
- e. To evaluate adverse events such as major bleeding, stroke, death and cognitive disorders (Mild Cognitive Impairment or dementia), on the long term, namely: 3 years.

Hypothesis:

- a. We expect to find a rate of known AF of approximately 20%, and to find newly detected AF in 4 to 5% of the screened population.

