- b. We expect to find a rate of paroxysmal AF of 45 to 60%.
- c. We expect that the baseline level of NTproBNP or BNP will be predictive of the development of new AF, especially when combined with the findings of the comprehensive geriatric assessment (CGA) and CHA₂DS₂Vasc score.
- d. We expect a rate of major bleeding of 3-5% per year.
- e. We expect that the ABC bleeding score, using age, GDF-15 and high sensitive Troponin T, will be predictive of major bleeding in the geriatric population.

Design:

- a. Prospective multicentre cohort study
- b. We aim to include 1250 geriatric ambulatory patients
- c. Inclusion period will last for 6 months, with a consecutive follow up period of 6 months, at 3 years patient files will be accessed for adverse events
- d. Scheduled commencement of the study is October 2020
- e. Blinding: none
- f. Randomization: none

Ethical board:

- a. The Commission Human Bound Research region Arnhem-Nijmegen, The Netherlands, has exempted the protocol as a 'niet WMO-plichtig onderzoek'.
- b. The record number of this decision is: 2019-5889.

Methods:

- a. The PPG measurements will be performed with a specially designed app, this research app will be developed by Happitech. Every participating center will receive a smartphone in order to install the application.

- b. All newly referred patients of 65 years and older that visit geriatric outpatient services are eligible (including Fall clinic, Memory clinic, Pre-operative geriatric assessment clinic, or any other geriatric outpatient clinics that are led by a geriatrician).
- c. Patients will be sent printed informative material about the project together with their appointment details. This material includes the informed consent form. They are asked to read the material, and fill out the informed consent form at home. At arrival to the outpatient clinic remaining questions will be answered, and the informed consent form collected, scanned, and added to their electronic medical file.
- d. Inclusion criteria:
 - a. The patient is able and willing to give written informed consent or allows a representative to do so in their name.
 - b. The paper copy will remain at the outpatient clinic to serve as a backup.
- e. Exclusion criteria:
 - a. The patient has a pacemaker or implantable cardioverter defibrillator.
 - b. The patient is known with a severe dementia, MoCA \leq 15 points.

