h. Frailty will be calculated as a Frailty Index, based on the accumulation of deficits model. It will incorporate a combination factors: functional, cognitive, physical and social. As proposed in literature (4. Searle et al., 5. Rockwood et al.), a number between 30 and 40 factors will be used to calculate the index. A detailed list of the variables and their definition is added as an attachment.

i. A detailed plan for the statistical analysis can be found on page 7 of this protocol.

j. Statistical analysis will be performed by [name], geriatrician at the Dijklander Hospital, and PhD student at the Free University in Amsterdam, under supervision of the principal investigators.

- k. First draft of the manuscript will be written by [name], geriatrician at the Dijklander Hospital, and PhD student at the Free University in Amsterdam, in collaboration with the principal investigators.
- l. Privacy: To protect patient privacy patients will be assigned a unique study code. The key to the code will be stored at a secure location at each hospital with limited access. Only coded data will be used for any data processing. The Board of Directors of the participating hospitals will be asked for approval the protocol. In addition, they will also be asked to appoint the research nurse for 0 fte (without salary) in their hospital.
- m. After 3 years, all patient files will be checked for the occurrence of: incident major bleeding, stroke, death or cognitive disorders (mild cognitive impairment or dementia + subtypes).

Figure 1. Study protocol

Laboratory Protocol

For the Dutch GERAF health care innovation project

As part of the Comprehensive Geriatric Assessment blood samples are taken. The number of measurements may differ between the participating centres, for example in which vitamins are analysed.

For the Dutch GERAF health care innovation project the standard laboratory testing should include measurement of:

Hemoglobin in mmol/L

eGFR in mL/min

TSH in mU/L

FT4 in pmol/L

Glucose in mmol/L

HbA1C in mmol/mol

INR

For study purposes one extra Lithium Heparine tube should be drawn, during the standard blood sampling.

This extra Heparine tube should be frozen at -20 degrees Celcius and stored after sampling at the participating centre.

The following extra analyses will be performed, for research purposes only:

GDF-15 in pg/mL

NT-proBNP in pg/mL

High sensitive Troponin T in ng/L

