All samples will be transported to the Dijklander Hospital and will be analysed there by the Diagnostic Centre West Friesland (DCWF).

After analysis, [name] will collect the outcomes and add them to the anonymised dataset.

Costs for the analysis and storage will be covered by Roche Diagnostics.

Statistical analysis plan

1. Automated generation of variables, based on collected data:

1. CHA₂DS₂VASc score
2. HAS-BLED score
3. ORBIT Bleeding Risk Score
4. ABC Bleeding Score
5. ATRIA Bleeding Risk Score
6. Class of impaired renal function

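### Read as a rule for choosing covariates, SAP 3.2's univariate significance screen is a weak method for about 40 to 50 expected cases of newly detected AF

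*Combined protocol and SAP*

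**What the plan says.** SAP 3.1 compares patients who stay in sinus rhythm throughout with those in whom AF is newly detected. It adds "Correction for age if necessary", without saying what makes correction necessary. SAP 3.2 consists of one line: "Correction/multivariate analysis of significant differences found in the univariate analysis 3.1". No significance threshold or list of variables is given.

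SAP section 4 then lists regression analyses. Item 4.1 is "Factors predicting newly detected AF", with no covariates and no selection rule. Item 4.2 is "NT-proBNP and/or GDF-15 predicting newly detected AF", which does name two biomarkers. Hypothesis c names an intended combination: NT-proBNP or BNP with the findings of the geriatric assessment and CHA2DS2-VASc. No SAP item turns that combination into a model. AUC is mentioned only for the bleeding scores (SAP 2.2).

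The number of cases is not stated and has to be derived. Hypothesis a expects "a rate of known AF of approximately 20%, and to find newly detected AF in 4 to 5% of the screened population", and the Design section aims for 1250 patients. Methods f excludes from analysis anyone with fewer than three PPG measurements.

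**The concern.** If significance in 3.1 decides what enters the multivariate model, the same few cases both choose the variables and estimate their effects. Three consequences are well known. Effects that survive the screen are overstated, real but moderate predictors are often missed, and the model looks better in its own data than it would in new patients. Age, an obvious candidate predictor of AF, could be left out on a judgement made after seeing the data.

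What is at stake is the set of predictor claims: 3.2, 4.1, and aim c (the predictive value of NT-proBNP) if the 3.2 rule is used there. The primary result, the rate of newly detected AF, does not depend on any of this.

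**Working it through.** **Expected cases.** The plan gives no case count to reproduce. From the Design section and Hypothesis a:
- Patients without known AF: 1250 × 0.80 = 1000. At 4% this gives 40 cases, at 5% it gives 50.
- Literal reading of the screened population (Methods g.o screens patients with known AF too): 1250 × 4% = 50 and 1250 × 5% = 62.5.
- If 20% are lost to the three-measurement rule (an assumption; no rate is given): 40 × 0.8 = 32 and 50 × 0.8 = 40 on the first reading; 40 and 50 on the second.

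**Candidate pool.** SAP section 1 ("Automated generation of variables, based on collected data") lists 11 variables. The Laboratory Protocol says "the standard laboratory testing should include measurement of" seven quantities, and adds three research assays: 11 + 7 + 3 = 21, before any item from the geriatric assessment. Four of these are bleeding scores that serve aim d, INR is collected only where applicable (Methods g.q), and three pairs overlap (eGFR and renal class, haemoglobin and anaemia, BMI and underweight). Removing them leaves 21 − 4 − 1 − 3 = 13. At 40-50 cases that is 1.9-2.4 cases per candidate with 21 (40/21, 50/21), or 3.1-3.8 with 13 (40/13, 50/13).

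**Simulation.** Assumptions, none from the documents: three real predictors with odds ratios 1.5, 1.3 and 1.2 per SD; 20 or 30 candidates in all, correlated at 0.2 or 0.4; screen at p<0.05, then a logistic model of whatever passed. The comparators are two five-term models fixed in advance. One holds all three real predictors; the other misses the OR 1.3 predictor. Optimism is apparent AUC minus true AUC. Results for 30 candidates at correlation 0.2 (1000 runs per row):

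| Patients, rate (cases) | Selected | Five terms, all real | Five terms, one missed | Median slope, same order |
|---|---|---|---|---|
| 1000, 4% (40) | 0.703 − 0.623 = 0.080 | 0.682 − 0.641 = 0.041 | 0.671 − 0.626 = 0.045 | 0.58 / 0.76 / 0.73 |
| 1000, 5% (50) | 0.699 − 0.629 = 0.070 | 0.682 − 0.645 = 0.037 | 0.669 − 0.629 = 0.040 | 0.62 / 0.79 / 0.76 |
| 800, 4% (32) | 0.712 − 0.614 = 0.098 | 0.690 − 0.637 = 0.053 | 0.679 − 0.622 = 0.057 | 0.52 / 0.71 / 0.67 |
| 800, 5% (40) | 0.705 − 0.622 = 0.083 | 0.685 − 0.641 = 0.044 | 0.672 − 0.625 = 0.047 | 0.57 / 0.75 / 0.71 |

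At about 62 cases, the most favourable count, optimism is 0.052 after selection against 0.023 for the complete fixed model, and the slope is 0.67 against 0.81. The choice of denominator therefore does not remove the difference.

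**Passing the screen.** A single predictor with a true OR of 1.3 per SD (4000 runs, same row order) passes in 36.4%, 43.6%, 29.5% and 35.5% of runs. When it passes, its mean reported OR is 1.55, 1.49, 1.62 and 1.55. A binary factor with 30% prevalence and a true OR of 1.5 passes in 25%, 29% and 34% of runs at 40, 50 and 62.5 cases. Its median estimate when selected is 2.19, 2.05 and 1.93.

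**Noise variables.** With 20-30 correlated candidates, at least one noise variable is significant in the final model in about 13-26% of runs. The fixed models also carry noise terms: 5 − 3 = 2 when complete and 5 − 2 = 3 when one real predictor is missed. They give 8-12% and 12-18%. As a rough check for independent terms, 1 − 0.95² = 9.8% and 1 − 0.95³ = 14.3%. With 13 candidates, selection gives 9-16%, about the same as the incomplete fixed model.

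**The case against.** The strongest objection is about meaning. Coming directly after the remark on age in 3.1, the line in 3.2 can be read as adjusting each significant group difference for confounding, rather than as building a model from the significant variables. Prediction has its own place in section 4, and no passage carries the 3.2 rule there. This stands. A reader might infer that the SAP commits its prediction models to univariate selection, but the documents do not say so. The optimism and calibration figures apply only if 3.2 is used as a covariate rule. If it is not, 4.1 is left without any rule, which on its own is missing detail rather than a wrong method.

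A reader might also infer that false predictors would dominate the results. That does not follow. It would require treating all 21 or more variables as independent candidates, while the plan's own lists overlap and include scores meant for bleeding. Against a fixed model that happens to miss a predictor, the excess risk of a significant noise variable is small and sometimes absent.

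Discrimination in new patients also changes little: across settings, the incomplete fixed model has a true AUC within −0.003 to +0.008 of the selected model. Finally, these are secondary analyses in an observational cohort, and 4.2 and Hypothesis c already name the main predictors. That limits the seriousness of the point, but it does not make the screen a good method.

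**Conclusion.** The point holds in a limited form. At 32 to about 62 cases, choosing covariates by univariate significance is a poorer method than a model fixed in advance from data already collected. With 20-30 correlated candidates, AUC optimism is about 0.05-0.10 against 0.02-0.06, and the calibration slope about 0.5-0.7 against 0.7-0.85. Moderate effects are usually missed and are overstated when found. The gain is in calibration and in honest estimates, not in materially better discrimination or far fewer false predictors. With about 13 candidates, the advantage over an incomplete fixed model largely disappears.

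These sizes rest on assumed effects, an assumed 0.05 threshold and assumed correlations, and the case count depends on which denominator the 4-5% refers to. The point ranks between a minor remark and a change that should be made. Nothing in it touches the primary detection rate.

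**What to change.** Replace the significance screen in 3.2 with one logistic model fixed before the outcome data are examined, and use it for 4.1 and 4.2 as well. Its terms are age (always included), the non-age CHA2DS2-VASc components as a score, Frailty Index, log NT-proBNP and log GDF-15. This is one reasonable way to put Hypothesis c and SAP 4.2 into practice, not the only one; leaving age out of the score avoids counting it twice but makes the score non-standard. Five terms give 40/5 = 8 to 50/5 = 10 cases per term, or 32/5 = 6.4 to 40/5 = 8 under the assumed 20% loss.

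Because even this model has a slope of only about 0.8 at 50 cases, fit it with ridge or another shrinkage method, with the penalty chosen by cross-validation. In simulation, ridge brought the slope near 1.0. Report bootstrap optimism-corrected AUC and calibration slope. For aim c, report NT-proBNP alone, and the same model with and without NT-proBNP, so that both its own and its added predictive value are shown. Label the other comparisons in 3.1 and 3.2 descriptive.

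The cost is SAP wording and modest extra analysis; all five terms are already collected. The downside is that fewer independent predictors can be claimed, and a real predictor outside the five terms is reported only descriptively.
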